#### Inclusion of Children

We will not include children younger than 18 years old in our study. Our criteria require postmenopausal status for inclusion into this study.

### **2.d Subject Recruitment Plans and Consent Process**

All new or newly diagnosed women with rUTIs receiving care at the Washington University Physicians Women's Center for Bladder and Pelvic Health who meet screening criteria will be approached. Existing rUTI patients that are not currently using D-mannose may also be approached. Enrollment may occur at any of the practice's four outpatient locations (Washington University Physicians' offices at: Center for Outpatient Health, Missouri Baptist Medical Center Women's Wellness Center, Center for Advanced Medicine - South County, and Barnes Jewish West County Medical Building). This study will involve only adult, postmenopausal women as rUTI predominantly affect this population. Recurrent UTI in men would be considered complicated and would not be addressed with a prophylactic treatment like d-mannose. In addition, men do not go through menopause and do not have a vagina and would thus not be treated with VET. Women meeting study criteria will be approached by a member of the research team for consent at the conclusion of the clinical visit during which the patient is screened eligible for the study. Women who meet RCT eligibility criteria except for a minimum of four weeks of VET use but are being started on VET for clinical indications will followup in approximately four weeks for a routine follow up clinical visit. These patients will be offered enrollment in the study at that time if they have been using VET for a couple weeks even if they aren't at the four week mark yet. However, their study day one cannot occur until they have been using VET for four weeks.

Eligible women interested in the study will have the study explained to them, the consent reviewed, and questions reviewed in a confidential manner in a private room. If the potential research participant would like to take the consent home with them to review before their next office appointment that will be allowed.

The following methods may be used to inform the public about our research study: letter and/or email to local and/or referring providers, Twitter, study flyers, news story or segment. Inclusion in this list does not guarantee that the method will be used, but instead allows for the method to be used. All of the methods would require a potential research participant to be referred to the office for care of their rUTI. A "Dear Doctor" letter and/or email to local and/or referring providers can be sent to referring providers to inform them of ongoing recurrent UTI research at the Washington University Physicians Women's Center for Bladder and Pelvic Health. Twitter posts will be limited to IRB-approved tweets and images. The Twitter posts will be able to link to the Washington University Physicians Women's Center for Bladder and Pelvic Health website (at [urogyn.wustl.edu](http://urogyn.wustl.edu)) to find out more about the Washington University Physicians Women's Center for Bladder and Pelvic Health. A study flyer would provide the Washington University Physicians Women's Center for Bladder and Pelvic Health name and phone number with information describing rUTI and that our research team is trying to

determine the benefit of non-antibiotic treatments to prevent recurrent urinary tract infections in menopausal women. These flyers could be distributed to local and/or referring providers with the “Dear Doctor” letter to display in their waiting room or offices. The flyer could also be displayed in break rooms at Barnes Jewish Hospital, Center for Outpatient Health, Center for Advanced Medicine, St. Louis Children’s Hospital, and St. Louis College of Pharmacy. The research team would like the opportunity to work with the Washington University School of Medicine Medical Public Affairs office to spread word about this study via a local television or radio as part of a news story or segment. The principal investigator would work with the Medical Public Affairs office to contact specific local reporters and pitch the story to them. There will not be an official news release. If any current subjects would like to share their experiences in the trial with the media for a news story or segment then all HIPAA protocol will be complied with. Subjects would be made aware that their care and participation in the trial would not be affected by their voluntary decision to share their experience, and that they do not have to share their story if they do not wish to.

[figure not shown]
## 2.e Randomization Method and Blinding

For the randomized, controlled trial portion of the study:

Allocation concealment will be in place to ensure the individual enrolling the subject into the study has no a priori knowledge of group assignment. Block randomization will occur with randomly mixed block sizes of 2, 4, and 6. The allocator will hide block size from the executor in order to prevent the executor from predicting the next assignment. Randomization will be carried out by having a piece of paper that has the phrase “Intervention (Nutraceutical + VET)” or “Control (VET only)” placed inside an envelope. The outside of the envelopes will be labeled with the sequence number. After a patient has been enrolled into the study and consented, the next sequence numbered envelope on the stack will be opened to determine the study group that the subject will enter.

For the observational portion of the study, no randomization or blinding will occur.

The diagram below outlines randomization details:

---

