### **3.e Subject Compliance Monitoring**

All participants will be asked to complete a simple weekly study diary. The 90 days of the study will be divided into 12 full weeks and 1 partial week for a total of 13 weeks of the diary. In the diary, one of the questions asked for each week of the study is number of doses missed each week. This study will use a text message service through the REDCap (Research Electronic Data Capture) database. During the 90 day study period, all study participants in both the RCT and Observational arms will receive text message reminders to complete their study diary for the week on study days 7, 14, 21, 28, 35, 42, 49, 56, 63, 70, 77, 84, and 90. This same text message will ask patients if any new symptoms were experienced in the past week and request a “Yes” or “No” response via text message. Study participant responses will automatically be entered in the REDCap (Research Electronic Data Capture) database for this study. If the study participant sends a “Yes” response by text message a member of the research team will contact the patient to follow up for more information about the symptoms. If they declined text messaging when enrolling in the study, the study participant will receive periodic phone calls with reminders to complete their study diary. The subject will be instructed to bring their study diary to each appointment.

Six weeks into the study, each study participant will receive a phone call from a member of the research team. During this phone call questions referencing compliance with completing the study diary, taking study medications as prescribed, if they have been treated for a UTI by anyone outside of our office during the study period, side effects noted, and if they have any questions to be answered will all be addressed.

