### 3.g Blinding of Study Drug

For the treatment arm of the RCT, the D-mannose powder will be ordered and distributed by the research team. The manufacturer label will be covered up/removed and a study label stating contents of a nutraceutical will be used to maintain patient blinding to which nutraceutical is being used. The research team will not be blinded to the study drug. There are no placebos being used in this study.

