## **G   Statistical Plan**

### ***G1   Sample Size Determination and Power***

We based our sample size estimate on assumptions for our primary aim, as this is the most important aim for providing information to support future recommendations and studies aimed at individualized patient care. The first published study on D-mannose was a RCT that showed 14.6% of rUTI patients develop another UTI while on treatment [9]. To be conservative in our sample size calculations, we assume 20% of patient on D-mannose will develop a UTI during the three-month treatment period. Very few studies have stated the percent of rUTI patients that develop another UTI while on vaginal estrogen therapy [27-29]. Due to the range of the published values, an average of these numbers was taken to arrive at an assumption that 45% of patients on only vaginal estrogen therapy will develop another UTI during the treatment period. We also accounted for a 10% dropout rate during the study period. Using these numbers to determine sample size, we calculated 60 patients would be needed per RCT arm for a total of 120 patients in the RCT. We recognize that our power for secondary aims is lower; however, we included these to begin to explore these other areas that are fundamental for understanding the underlying mechanism of D-mannose and how it works with rUTI. We have decided to also enroll 60 patients in the Observational arm of the study.

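### Section 2.e promises allocation concealment but relies on numbered paper envelopes, with no seal, custody or opening record described for the four offices; release from the existing REDCap database would be safer at little cost.

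*Combined protocol and SAP*

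**What the plan says.** Section 2.e (Randomization Method and Blinding) states that the person enrolling should not know the assignment in advance. It gives three supports for this: block sizes of 2, 4 and 6 in random order, an allocator who keeps the block size from the executor, and opening only after enrolment and consent. The device is a paper slip in an envelope with a sequence number on the outside, and "the next sequence numbered envelope on the stack will be opened to determine the study group that the subject will enter".

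Section 2.d says: "Enrollment may occur at any of the practice's four outpatient locations". It also says that a member of the research team seeks consent.

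Section 3.g says: "The research team will not be blinded to the study drug. There are no placebos being used in this study". Section G2, in the context of the interim analysis, says instead that the investigators stay blinded to assignment.

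On infrastructure, section 3.e says: "This study will use a text message service through the REDCap (Research Electronic Data Capture) database". Section H2 provides REDCap training for the staff who will use it.

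**The concern.** Concealment depends on what physically prevents someone from learning or changing the next assignment before a woman is committed to the trial. The text of 2.e gives a rule (open after consent) but no means of showing that the rule was kept. It mentions no seal or opacity, names no holder or opener, and describes no entry of a study ID, date or signature before opening and no reconciliation. It also does not say how the stack serves four offices. The stack could be shared, split by office or read out by telephone, and each arrangement needs different controls.

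Hidden mixed blocks address a different threat, which is guessing from past assignments. They give no protection if a slip can be seen through the paper, opened early or moved to another woman.

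The stake is selection bias. If women at higher risk of UTI went preferentially to one arm, the arms would differ before treatment began. With no placebo and a research team that is not blinded to the study drug, concealment at entry carries much of the weight of the randomized comparison. A preference for one arm is plausible, since section 2.f notes that the clinic already recommends D-mannose daily to patients outside the study.

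**Working it through.** **1. The plan's own figure (G1).** Inputs: for the D-mannose arm, "we assume 20% of patient on D-mannose will develop a UTI during the three-month treatment period"; for the control arm, "45% of patients on only vaginal estrogen therapy will develop another UTI during the treatment period"; a dropout allowance of 10%; and as the result, "60 patients would be needed per RCT arm for a total of 120 patients in the RCT". Alpha and power are not stated, so two-sided 5% and 80% are assumed. With pooled variance, the mean proportion is (0.45 + 0.20)/2 = 0.325, and

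n = [1.960 × √(2 × 0.325 × 0.675) + 0.842 × √(0.45 × 0.55 + 0.20 × 0.80)]² / 0.25² = 53.9, so 54 per arm.

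Allowing for dropout, 54/0.90 = 60 per arm, which agrees with the plan. The allocation method does not affect this number. The 54 evaluable per arm is used below.

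**2. What hidden blocks do and do not achieve.** A simulation used 20,000 runs of 120 women, with the three block sizes assumed equally likely and a guesser who sees all past assignments and always names the arm that is behind.

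| Situation | Result |
|---|---|
| One stack of 120: guess correct | 70.2% |
| Four stacks of 30: guess correct | 69.9% |
| Next assignment certain because imbalance has reached 3, sizes hidden | 0.8% of women |
| Next assignment certain, block boundaries known | about 32% of women |

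Chance is 50%. Hiding the sizes makes certainty rare, although guessing stays better than chance. Splitting the stack by office hardly changes this. The remaining exposure is the physical slip, which these figures do not address.

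**3. How large a bias could be.** The plan gives no spread of risk and no steering rate, so both are assumptions. Suppose there is no treatment effect, half the women have a 90-day risk of 0.45 + h and half 0.45 − h (averaging the plan's 45%), and a share s is steered, with high-risk women to control and low-risk women to D-mannose. Then

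- control risk = 0.45 + h × s
- D-mannose risk = 0.45 − h × s
- spurious difference = 2 × h × s.

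For a 60%/30% split, h = 0.15. For example, s = 0.10 gives 0.465 against 0.435, a difference of 3.0 points. For a 50%/40% split, h = 0.05. The table gives the exact rejection probability of the two-sided 5% Pearson chi-squared test with 54 per arm.

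| Share steered | 60/30: difference (points) | 60/30: two-sided rate | 60/30: rate favouring D-mannose | 50/40: difference (points) | 50/40: two-sided rate |
|---|---|---|---|---|---|
| 0% | 0 | 4.5% | 2.2% | 0 | 4.5% |
| 10% | 3.0 | 5.5% | 4.5% | 1.0 | 4.6% |
| 20% | 6.0 | 8.8% | 8.4% | 2.0 | 5.0% |
| 30% | 9.0 | 14.4% | 14.3% | 3.0 | 5.5% |

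Steering in the opposite direction would give the mirror image, a bias against D-mannose.

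**The case against.** The strongest reply is that the plan does more than this point might suggest. It states concealment as an aim, hides mixed block sizes, separates allocator from executor and opens envelopes only after consent. Well-run envelopes are an accepted method. Four stronger readings are tempting, and the documents do not support them.

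- *The recruiting team handles the envelopes.* Section 2.e identifies neither the allocator nor the executor, and section 2.d says only who seeks consent. Equally, nothing says the executor is independent of recruitment.
- *One physical stack is shared by four offices.* This rests on a singular noun. The number and location of stacks are not stated, and separate stacks would still be randomized.
- *Tampering would leave no trace.* Sequence numbers can reveal an envelope skipped or used out of order. Each woman has a study ID (H1), and K3 lists a screening log and an enrolment form. A sequence number would not reveal an envelope inspected early, and no link from sequence number to study ID is described. The supportable statement is that the text specifies no audit trail. The randomization diagram is not shown, so even this is limited to the text.
- *The bias could not be detected or removed.* Section G3 compares potential confounders between arms and adjusts if they differ appreciably. Steering on recorded factors could be partly seen and adjusted for. Steering on unrecorded risk would escape.

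It is also fair to object that the calculation assumes error-free sorting by risk and that no passage supports any steering rate. The 50/40 column shows how small the effect can be. What stands is that concealment is promised while the text leaves out the controls that would secure it.

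**Conclusion.** The point holds as a weakness in how concealment is secured. It is not evidence that assignments were or will be subverted. The text of 2.e does not show how its stated aim is delivered across four offices, in a trial with no placebo and a research team unblinded to the study drug.

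The size is unknown. Over 10 to 30% steering, the two-sided false-positive rate ranges from barely changed (4.6%, 50/40 split) to about three times the unsteered rate (14.4% against 4.5%, 60/30 split). These figures rest on the assumed risk splits, perfect sorting, 54 evaluable women per arm and no true effect. The sample size is unaffected. A more secure method is available at small cost, so the change is worth making even though the bias may be nil.

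Separately, 3.g and G2 give different accounts of whether the study team is blinded, and they must be reconciled.

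**What to change.** In section 2.e, replace the envelope stack with one randomization list, keeping the hidden mixed blocks, loaded into the trial's REDCap database by the allocator. State that the allocator does not recruit. Release the assignment, with a time stamp, only after the woman's study ID, consent and confirmed eligibility have been saved. The same list then serves all four offices.

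If envelopes stay as a back-up, specify that they are sealed and opaque, that study ID, date and signature are written on the unopened envelope, and that the allocator holds them and reconciles them against the enrolment log.

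Align 3.g and G2 by stating who is blinded, to what, and at which stage.

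The cost is a short amendment, set-up and testing of the randomization function (the documents do not show that it is already configured), designation of a non-recruiting list holder, and database access at the enrolment visit. No extra participants or visits are needed.

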## 2.f Risks and Benefits

D-mannose is a nutraceutical sold over the counter solely for the prevention of UTI. It falls under the category of dietary supplements regulated by FDA under the Dietary Supplement Health and Education Act of 1994 (DSHEA) [24]. This is a different set of regulations than the regulations used for conventional food and drug products [24]. Risks associated with D-mannose use are believed to be mainly related to gastrointestinal side effects (bloating, loose stool, and diarrhea). Other possible side effects can include but are not limited to hypersensitivity or allergic reactions (acute skin or pulmonary changes). These side effects would be the same for subjects enrolled in this study as for patients not enrolled in this study that we recommend D-mannose prophylaxis to on a daily basis. Other potential risks of the study include participants may feel uncomfortable or be inconvenienced by filling out study related papers. They may prefer to obtain treatment for UTI-like symptoms from an urgent care or other outside provider. However, all rUTI patients in our office (no matter if enrolled in the study or not) are instructed to call our office when they experience UTI-like symptoms since our clinical practice is to obtain (when possible) urine cultures prior to initiating treatment and to have our patients followed primarily through our office for their urinary tract infections.

A potential benefit is the decreased incidence of rUTI among patients randomized to D-mannose in the randomized, controlled trial portion of the study or patients in the observational arm of the study. Otherwise, benefits for the participant are no different than if they were recommended D-mannose as part of their routine clinical care as a patient without being enrolled in the study. There is a global benefit of increased knowledge surrounding the utility of non-antibiotic prophylaxis for rUTI.

## 2.g Early Withdrawal of Subjects

At the time of consent, participants will be informed that their participation in this research is voluntary and that they may discontinue participation without penalty at any time.

## 2.h When and How to Withdraw Subjects

Withdrawal of subject as the result of subject decision:

- A subject enrolled in the study may decide to withdraw from the research at any time by notifying the principle investigator and/or another member of the research team by calling the office at [contact] and letting the office staff know she needs to speak to the principle investigator and/or member of the research team. The investigator speaking with the subject will clarify whether the subject wishes to withdraw from all components of the trial or only from a particular component of the trial. If the latter is desired, then follow-up data collection activities, for which the subject previously gave consent may continue.
- If a subject withdraws from the study then a member of the research team will ask the subject if she is willing to complete an study exit survey and/or the information that would have been gathered at the originally planned 3 month follow up appointment. This exit survey and 3 month follow up visit information may be obtained by appointment, by phone, or by mail.

Withdrawal of subject as the result of investigator decision:

- If an investigator terminates a subject's participation in the trial, the investigator should explain to the subject the reasons for this action and, as appropriate, other treatment options.
- If subjects were to have a serious adverse reaction to the medication, the investigator would recommend discontinuation of medication.

---

- An investigator may terminate a subject's participation in the study to protect a participant from excessive risk or risk with demonstrated lack of benefits or to maintain integrity of the data (for instance if a participant is not following study procedures or may be deliberately providing false information).
- If a subject is treated for an acute UTI during the 90 day study period without having an urine culture performed then data will be assessed both as if she did and did not have an acute UTI. She does not need to be withdrawn from the study as of the date of treatment of subjective UTI.. Antibiotics used for reasons other than UTI do not require subject withdrawal. Data obtained for any subject to the point of study withdrawal may be used in the study.
- If a subject is withdrawn from the study then a member of the research team will ask the subject if she is willing to complete an study exit survey and/or the information that would have been gathered at the originally planned 3 month follow up appointment. This exit survey and 3 month follow up visit information may be obtained by appointment, by phone, or by mail.
- Subjects lost to follow up will be presumed to not have an acute urinary tract infection from the time of last contact.

## **2.i Data Collection and Follow-up for Withdrawn Subjects**

Data collected prior to participant withdrawal may be retained and used including Protected Personally Identifiable Information (PPII) in a manner that is consistent with the study purpose and procedures as noted in this protocol and supplemental documents, unless the study participant notifies the primary investigator that all participant information must be removed from the study. All subjects that withdraw or are withdrawn from the study will be asked if they would be willing to complete an exit survey or the questions from the 3 month follow up visit form. The purpose of the exit survey would be to obtain information such as the "spot checks" that are built into the 3 month follow up/end of study form and to find out more information about why the subject decided to withdraw. This exit survey would be completed in clinic (at their next scheduled appt), by phone, or by mail.

